#### **7.4 Stopping Rules**

Interim analysis will be performed after enrollment of 6 patients. The stopping rules for study includes grade 3 acute toxicity in >30% of enrolled patients, and tumor progression/growth in >50% of enrolled patients.

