## 9.0 STATISTICAL CONSIDERATIONS

### 9.1 Study Design/Study Endpoints

This is an open label single-arm phase II non-randomized prospective single arm study that treats a single SRM with SABR. The primary objective is local control of the SRMs. Local control is defined as less than 4mm increase in the longest diameter of tumor measured using either MRI or contrast enhanced CT scan and with no radiographic or pathologic evidence of viable tumor. The endpoint will be measured at a minimum follow up of one year. Secondary objections and endpoints explore the safety, toxicity, growth, growth rate, local failure, IDR, immune response and progression of the SRMs after SABR.

The stopping rules for this study include any treatment-related >grade 3 toxicity. If there are any treatment related grade 3 acute toxicity in >30% of enrolled patients after enrollment of at least 6 patients, the study will be suspended until permitted by a safety review.

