## 9.2 Sample Size and Accrual

There is no reliable historic information on local control rate of SABR for primary RCC since the retrospective studies have used a wide range of SABR dose fractions and varying definitions of local failure. From the retrospective studies and one phase I trial, we found three local failures out of 34 patients (section 1.3). Thus, it is expected that the local control rate will be at least 90% in this trial. With a sample size of 16 patients, the standard error of local control rate will be at most 7.5% with a 95% confidence interval of 15%, since the local control rate is expected to be at least 90%.

A sample size of 16 patients in this single-arm phase II trial will have more than 90% power to detect the difference between 100% pre-treatment tumor growth and 50% post-treatment tumor growth using a two-sided binomial test with a 0.05 significance level. With the sample size of 16 patients in this single-arm phase II trial, a single group t-test with a two-sided 0.10 significance level will have 80% power to detect the difference between a pre-treatment tumor growth rate of 0.4 cm/year and a post-treatment tumor growth rate of 0.16 cm/year (a 60% reduction), assuming that the standard deviation is 0.36 cm/year. The power calculations were conducted using the software PASS 12.

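### The power of more than 90% at 50% post-treatment growth is a single-stage figure; with the Section 7.4 growth stopping rule applied once to six known outcomes, and a stop counted as non-success, it is about 66%

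*Protocol*

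**What the plan says.** Section 9.2 gives a power statement: a sample of 16 patients "will have more than 90% power to detect the difference between 100% pre-treatment tumor growth and 50% post-treatment tumor growth", with the comparison made "using a two-sided binomial test with a 0.05 significance level". The paragraph mentions no interim look.

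Section 7.4 adds one: "Interim analysis will be performed after enrollment of 6 patients". It lists two stopping criteria. One is grade 3 acute toxicity in more than 30% of enrolled patients. The other is "tumor progression/growth in >50% of enrolled patients".

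Section 9.1, in the statistics chapter, repeats stopping rules for toxicity only. For its rule on grade 3 acute toxicity it adds that "the study will be suspended until permitted by a safety review". It does not mention the growth rule. It also says of the primary endpoint: "The endpoint will be measured at a minimum follow up of one year".

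Nowhere does the protocol say that the power allows for the growth rule, that the rule is non-binding, or how a stopped study would be analysed.

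**The concern.** The power figure and the stopping rule stand in the same protocol but describe different designs. Section 9.2 assumes that all 16 patients are always observed. Section 7.4 allows the study to end after six if most tumours have grown. At a true growth proportion of 50%, the expected count among six patients is three and the rule acts at four, so chance alone will often trigger it.

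An ethics board or monitoring committee reading Section 9.2 would therefore believe that a treatment which halves the proportion of growing tumours is very likely to be recognised as effective. Under the plain reading of Section 7.4, such a treatment would lead to a stop for growth in about one trial in three.

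**Working it through.** **Inputs.** n = 16, null growth 100%, alternative growth 50%, two-sided binomial test at 0.05 (Section 9.2). One look at six patients, stop if more than 50% grow, so at least 4 of 6 (Section 7.4).

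**Step 1: reproduce the printed power, no interim.** Count non-growers among 16 and reject when there are at least r.

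- Null of exactly 100% growth: one non-grower contradicts it, so r = 1 and power = 1 − 0.5^16 = 99.998%.
- The null may have been entered in the software as slightly below 100%. Null non-growth rates from 0.1% to 10% give r from 1 to 5. Power is 99.998%, 99.97%, 99.8%, 98.9% and 96.2% for r = 1 to 5.

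All exceed 90%, so the printed figure reproduces as a single-stage calculation.

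**Step 2: stopping probability at 50% growth.** With all six outcomes known:

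P(at least 4 of 6 grow) = (15 + 6 + 1)/64 = 22/64 = 34.4%.

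**Step 3: power with the rule, a stop counted as non-success.**

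Power = sum over g = 0 to 3 of [C(6,g)/64] × P(at least r − (6 − g) non-growers among the remaining 10).

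- r = 1 to 3: every continuing trial already has at least 3 non-growers, so each second factor is 1 and power = 42/64 = 65.6%.
- r = 4: 42/64 − (20/64)(1/1024) = 65.6%.
- r = 5: 42/64 − (20/64)(11/1024) − (15/64)(1/1024) = 65.3%.

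The stopping rule sets the ceiling, so the result hardly depends on the rejection region used.

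**Step 4: other true growth proportions, same assumptions (r = 1 to 4).**

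| True growth | P(stop at six) | Power with the rule |
|---|---|---|
| 50% | 34.4% | 65.6% |
| 40% | 17.9% | 82.1% |
| 30% | 7.0% | 93.0% |
| 20% | 1.7% | 98.3% |
| 10% | 0.1% | 99.9% |

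**Step 5: fewer outcomes known at the look.** Section 7.4 times the look by enrolment and uses enrolled patients as the denominator. With growers still divided by six, at 50% growth:

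- 5 assessed: P(at least 4 of 5) = 6/32 = 18.8%
- 4 assessed: P(4 of 4) = 1/16 = 6.3%
- 3 or fewer assessed: the rule cannot act, 0%

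With r = 1, the corresponding power is 100% − 18.8% = about 81%, 100% − 6.3% = about 94%, and essentially unchanged.

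**The case against.** **There is no arithmetic error.** This stands. The printed figure is correct for a fixed sample of 16; the fault is that it does not describe the design with the interim rule.

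**The 66% depends on when the look happens.** This also stands. Scans are six-monthly (Sections 5.3 and 5.4) and the primary endpoint needs at least a year, so at the sixth enrolment some patients may have no growth result. With four or fewer assessed, power above 90% survives. The protocol does not say whether the look waits.

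**A stop need not be a failed test.** Against a literal null of 100% growth, 21 of the 22 stopping outcomes (4 or 5 of 6 growing) already contain a non-grower. If stopped trials were tested on the data in hand, rejection at 50% growth would have probability 63/64 = 98.4%, or 57/64 = 89.1% if two non-growers were required at the stop. Counting a stop for growth as non-success is the usual convention and the natural reading, but it is a convention that the protocol does not state.

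**The two criteria might have to be met together.** They are joined by a conjunction, and a joint requirement would make stopping rarer. The sentence reads more naturally as a list, and Section 9.1 uses the toxicity criterion on its own.

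**The sponsor expects far less growth than 50%.** True. Section 9.2 expects local control of at least 90%, and Section 6.1.4 makes absence of tumor growth a condition of local control, so expected growth is at most 10%, where the rule costs almost nothing. The planned analysis in Section 9.3 is mainly estimation. This limits the consequence, but 50% is the alternative at which the protocol chose to print its power.

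**Stronger readings that the documents do not support.** A reader might infer that the growth rule is re-checked after every patient from the sixth onward, which would raise the stopping rate. Section 7.4 describes one interim analysis, and the open-ended wording about at least six patients in Section 9.1 concerns toxicity only. A reader might also take the power as the chance of completing the trial. Power is the probability of rejecting the null, and Section 9.2 claims nothing about completion.

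**Conclusion.** The point holds in conditional form. The power in Section 9.2 belongs to a single-stage design and does not account for the growth rule in Section 7.4. At the 50% alternative, stopping has probability 34.4% and power is about 66%, at least 24 points below the stated 90%. Three assumptions carry this result: one look, all six growth outcomes known at that look, and a binding stop counted as non-success.

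The documents do not support an unconditional statement that power is 66%, because Section 7.4 leaves the timing of the growth reading and the consequence of a stop open. Nor do they support calling the trial undersized: at the expected growth of 10% or less, the rule leaves power at about 99.9%. What is established is that Sections 7.4, 9.1 and 9.2 do not describe the same design, and that under the plain reading the printed power is materially too high at the alternative quoted.

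**What to change.** Restate the power in Section 9.2 with the Section 7.4 rule included and the assumptions written out. For example: with one look when the first six patients all have a growth outcome, and a stop for growth counted as non-success, the study stops with probability 34% and has about 66% power at 50% post-treatment growth; the figures are 7% and about 93% at 30% growth; at 10% growth the stopping probability is about 0.1%.

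Alternatively, quote the power at the growth proportion that the sponsor expects (about 10% or less) and note that the interim rule costs about 0.1 point there.

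In either case, reconcile Sections 7.4, 9.1 and 9.2 on whether the growth rule applies, when growth is read for it, and how a stopped study is treated in the analysis. If the look does not wait for six growth outcomes, the 34% and 66% must be recalculated for the timing that is adopted.

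The cost is a few sentences in an amendment and a less favourable figure at the 50% alternative. No patients are added, and the stopping threshold and sample size stay as they are.

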**STUDY SCHEMA**

**STUDY SUMMARY**

Title	Stereotactic Ablative Radiation Therapy (SABR) for patients with primary Renal Cancer (RCC)
Short Title	SABR for primary RCC
Protocol Number	The standard protocol number used to identify this study
Phase	Phase II
Methodology	Single arm open label
Study Duration	5 years
Study Center(s)	Single-center
Objectives	To eliminate growth and viable tumor in biopsy proven small primary RCC by SABR
Number of Subjects	16
Diagnosis and Main Inclusion Criteria	biopsy proven and growing small primary RCC
Study Product(s), Dose, Route, Regimen	Stereotactic Ablative Radiation Therapy (SABR): 3 fractions of 12Gy, or 4 fractions of 10Gy or 5 fractions of 8 Gy
Duration of administration	1-3 Weeks.
Reference therapy	Lesion growth is being compared to pre-treatment growth
Statistical Methodology	Exact binomial test

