Based on the published retrospective and the two prospective phase I trials, the dose fractionations evaluated in this trial is 8Gy x 5, 10Gy x 4 and 12 Gy x 3. In a retrospective study published paper by Wersäll, et al, from the Karolinska Hospital, 50 patients with kidney cancer, both primary and metastatic, were retrospectively analyzed [50]. High rates of local control were achieved with doses ranging from 25 Gy to 45 Gy. The most common doses used were 40 Gy in 5 fractions and 45 Gy in 3 fractions. Another retrospective study used the dose of 40Gy in 5 fractions and both studies reported excellent control rate [45]. Therefore 8Gy x 5 is evaluated in this study. The 4 and 3 fraction equivalent doses to this dose levels are 10Gy and 12 Gy respectively, which are the two other dose levels included in this trial. Justification of the three fraction dose equivalent of 12Gy x 3 comes from the phase I study that did not see any failures at this level.

The study population for this trial is patients with biopsy proven primary RCC that are candidates for active surveillance (AS). Keeping patient safety in perspective, it is reasonable to offer an experimental treatment such as this to a patient population that would have otherwise been put in AS. At any sign of progression, the patients that have undergone SABR in this trial will be offered the standard of care (SOC) of radical nephrectomy, partial nephrectomy or ablation as deemed appropriate by the treating urologist—which is same as what would have been offered to them had they been in AS. The AUA defines AS patients to be those with small renal mass (SRM) with <3cm tumors. The NCCN recommends AS for patients with T1a tumors or tumors <4 cm. A number of retrospective and one prospective study reported on the natural history of SRMs [51-55]. A meta-analysis reviewed multiple retrospective studies and reported an average growth rate of 0.28 cm/year for these tumors [51]. They further reported a growth of 0.4 cm/year in the subset of patients that had biopsy confirmed RCC. Keeping clinical application in perspective, it is logical to use SABR only to tumors that are growing, since one third of the SRMs do not grow. Therefore, patients

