**5.1.15 Tumor assessment**

Tumor assessment will be performed using MRI with (preferred) or without contrast, or contrast enhanced CT. A growth of >2mm of tumor size within one year period must be demonstrated to meet be eligible for this study.

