#### **6.1.4 Response Criteria**

##### **6.1.4.1 Evaluation of Lesions**

Complete Response (CR): Disappearance of all target lesions. Disappearance of all target lesions. Any pathological lymph nodes (whether target or non-target) must have reduction in short axis to <10 mm (the sum may not be "0" if there are target nodes). Determined by two separate observations conducted not less than 4 weeks apart. There can be no appearance of new lesions.

Partial Response (PR): At least a 30% decrease in the sum of the longest diameter (LD) of target lesions, taking as reference the baseline sum LD. There can be no appearance of new lesions.

Progressive Disease (PD): > 20% increase in the SLD taking as reference the smallest SLD recorded since the treatment started (nadir) and minimum 5 mm increase over the nadir.

Stable Disease (SD): Neither sufficient shrinkage to qualify for PR nor sufficient increase to qualify for PD, taking as reference the smallest sum LD since the treatment started. There can be no unequivocal new lesions.

Tumor Growth (TG): At least a 4mm increase in the LD of treated lesion in a single scan when compared to baseline scan (or an increase of >2.0mm in two consecutive scans).

Local Control: No TG AND a complete radiographic or pathologic absence of tumor viability.

Local Failure: Any TG OR any radiographic or pathologic evidence of tumor viability.

Indeterminate Disease Response: (IDR): 1) Presence of radiographic evidence of viable disease without any increase in the LD (<4mm) sufficient enough to qualify for TG; 2) complete absence of radiographic evidence of viable disease regardless of any change in tumor diameter.

A biopsy is recommended in the case of tumors with ≥4mm increase in size with no radiographic evidence of viable tumor, OR any tumors with radiographic evidence of viable tissue.

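### The power statement for 100% against 50% tumour growth uses a null set by the entry criterion, so it neither justifies 16 patients nor supports an efficacy conclusion

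*Protocol*

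**What the plan says.** Protocol section 9.2 gives three supports for 16 patients: a precision statement for the local control rate, a binomial power statement on growth, and a t-test on growth rate. This point concerns the second, which claims power above 90% for this comparison: "the difference between 100% pre-treatment tumor growth and 50% post-treatment tumor growth using a two-sided binomial test with a 0.05 significance level".

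The other relevant places are:
- **Entry (sections 3.1.4 and 5.1.15):** "A growth of >2mm of tumor size within one year period must be demonstrated". The Study Summary names pre-treatment growth as the reference and gives the method as "Exact binomial test".
- **Growth after treatment (section 6.1.4.1):** "At least a 4mm increase in the LD of treated lesion in a single scan when compared to baseline scan", or, as the second limb of the rule, more than 2.0 mm on two consecutive scans.
- **Timing:** section 9.1 measures the endpoint at a minimum of one year; section 5.3 schedules scans every six months.
- **Natural history (section 1.3):** a mean of 0.4 cm/year in biopsy-confirmed RCC. Growing tumours are selected "since one third of the SRMs do not grow".
- **Analysis (section 9.3):** local control and the proportion without growth are estimated with exact 95% confidence intervals. No null value is given.

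**The concern.** The null of 100% is true by selection. Every enrolled tumour has grown more than 2 mm in some year before entry, but that does not mean every untreated tumour would meet the growth rule in the following year. Growth rates vary over time, measurements carry error, and the 12-month rule is stricter than the entry rule. A steady 3 mm/year tumour counts as growing at entry. At six and twelve months it measures +1.5 mm and +3.0 mm, which meets neither limb of the post-treatment rule.

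A null of exactly 100% also has no variance, so a single exception rejects it. If the power sentence is taken at face value, a report could present rejection as evidence that SABR works, when a few tumours not growing is roughly what surveillance alone might show. The sentence also covers growth only. The primary endpoint, local control, additionally requires no radiographic or pathologic evidence of viable tumour.

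**Working it through.** **1. The stated power.** Inputs from section 9.2: n = 16, null growth proportion 1.00, alternative 0.50. Under the null all 16 tumours grow, so the test rejects if at least one does not.
- Power = 1 − 0.5^16 = 99.998%. The claim of more than 90% is arithmetically true.
- With n = 4: 1 − 0.5^4 = 93.75%. The sentence therefore does not lead to 16.
- Softening the null hardly changes this. At n = 16 and 0.025 in the lower tail, power at 50% growth is 99.97% for a null of 0.99 and 96.2% for 0.90.

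**2. Rejection when treatment does nothing.** Let q be the chance that an untreated, enrolled tumour does not meet the growth rule. Then P(reject) = 1 − (1 − q)^16.

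| q | P(reject) |
|---|---|
| 1% | 14.9% |
| 5% | 56.0% |
| 10% | 81.5% |
| 20% | 97.2% |
| 29.7% | 99.6% |
| 50% | 99.998% |

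**3. Plausible q at 12 months.** Assume growth rates are Normal with mean 0.4 and SD 0.36 cm/year. The mean is in section 1.3. The SD is stated only for the t-test in section 9.2, and its use for untreated growth is an assumption. With linear growth, six-monthly scans and each scan compared with baseline, both limbs require at least about 0.4 cm/year to be met by 12 months.
- Entry rate carries no information about later rate: q = P(rate < 0.4) = 50%.
- Entry rate persists fully, given more than 0.2 cm/year at entry: q = (0.500 − 0.289) / (1 − 0.289) = 29.7%.

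Across this range an inactive treatment rejects with probability 99.6% to 99.998%.

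**4. Longer follow-up.** The two-scan limb now matters. At 18 months it is met by any rate above 0.2 cm/year (the 12- and 18-month scans both exceed 2 mm). At 24 months the required rate is 0.2/1.5 = 0.133 cm/year (18- and 24-month scans). Let entry and follow-up rates be bivariate Normal with correlation r, conditional on an entry rate above 0.2. Then q = P(follow-up rate below the threshold | entry rate > 0.2).

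| r | q, 18 mo | P(reject) | q, 24 mo | P(reject) |
|---|---|---|---|---|
| 0 | 28.9% | 99.6% | 22.9% | 98% |
| 0.5 | 19.7% | 97% | 14.6% | 92% |
| 0.8 | 12.2% | 88% | 7.8% | 73% |
| 1 | 0% | 0% | 0% | 0% |

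The last row requires perfect persistence and no measurement error.

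**5. The other two supports in section 9.2.**
- Precision: √(0.9 × 0.1 / 16) = 0.075, as stated.
- t-test: effect (0.40 − 0.16)/0.36 = 0.667, noncentrality 0.667 × √16 = 2.67, 15 degrees of freedom, two-sided 0.10. Power is 81.6% against the stated 80%.

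Neither depends on the 100% null.

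**The case against.** The strongest reply is that nothing is decided by this test. Section 9.3 plans estimation, no success threshold appears anywhere, and the sample size has two other supports that reproduce. This stands, and it limits the severity. A reader might infer that the protocol sets a success bar of one non-growing tumour in 16. It does not: that is only the rejection region implied by the power sentence.

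The second reply is that the growth rule has two limbs and that one year is only the minimum follow-up. By 18 months the 3 mm/year tumour measures +4.5 mm and counts as growing under both rules. This also stands. A reader might infer that an inactive treatment would reject almost surely at any follow-up, or that 50% growth is simply what no effect would produce. The documents do not support either in general. Near-certainty holds at 12 months under the stated assumptions, and the 50% figure needs both a 12-month cut and no persistence of entry growth. The statement that one third of small renal masses do not grow describes unselected masses and cannot be used directly for enrolled patients.

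The third reply is that the primary endpoint is protected, because local control also requires no viable tumour and a one-year biopsy is required. A reader might infer that the trial's main result cannot separate SABR from surveillance. That goes too far: the weakness lies in the growth-only power statement.

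None of this rescues the sentence. The protocol itself fixes the null, alternative, test and significance level, so the matter is not one left to a later analysis plan.

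**Conclusion.** The point holds at moderate severity. The power figure is not a calculation error; the fault is the null hypothesis. A null of 100% growth follows from the entry criterion, is rejected by one tumour in 16, and gives 93.75% power with four patients. The sentence therefore justifies neither the sample size nor any claim of efficacy.

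The probability that an inactive treatment rejects is above 99% at 12 months and about 73% to 99.6% at 18 to 24 months for correlations of 0 to 0.8. It reaches about zero at those later times only with perfect persistence and no measurement error. These figures rest on Normal, linear growth, on the SD of 0.36 cm/year applying to untreated tumours, and on comparing each scan with baseline. The 99.998% and 93.75% need none of these assumptions.

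**What to change.** Delete the 100% against 50% power sentence from section 9.2, and rest the 16 patients on the precision of the local control rate and the growth-rate t-test. This changes wording only; the sample size and the analyses in section 9.3 stay as they are.

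If a test of the growth proportion is wanted, set its null to the proportion of untreated tumours expected not to grow under the same post-treatment rule at a fixed 12 months. State the assumption and its range. Exact binomial cut-offs for n = 16, each the smallest with one-sided alpha at or below 0.025:

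| Null (no growth) | Success if not growing | One-sided alpha | Power at true 90% | Power at true 75% |
|---|---|---|---|---|
| 0.50 | ≥13 of 16 | 0.011 | 93% | 40% |
| 0.40 | ≥11 of 16 | 0.019 | 99.7% | 81% |
| 0.30 | ≥10 of 16 | 0.007 | 99.9% | 92% |

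Do not carry a cut-off derived from growth over to local control, which also requires absence of viable tumour and would need its own null.

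The cost of this second option is less favourable stated power at moderate true rates, most visibly 40% at a true 75% under the 0.50 null. It also adds a success criterion to a protocol already in its ninth version, which is more than a wording change.
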